Gait impairments in PD are often resistant to treatment, particularly as the disease progresses. Therefore, insight in the pathophysiology of gait disturbances is essential for improving treatment options and quality of life for PD patients. Our study will answer the question of whether cerebellar hyperactivity alleviates or worsens gait deficits in PD patients. If cerebellar hyperactivity in PD is compensatory, anodal (i.e. excitatory) tDCS should improve gait in PD patients, whereas cathodal (i.e. inhibitory) tDCS will make matters worse. In contrast, if cerebellar hyperactivity is pathological, cathodal tDCS will improve gait and anodal tDCS will worsen it. Hence, our study will improve our fundamental understanding of gait pathophysiology in PD patients. We will focus on the aspects of gait that are particularly affected in PD and associated with fall risk, such as stride length and gait speed (Paul et al. 2013). In this way, our study may identify the cerebellum as a potential new target for treatment, opening up new possibilities improving gait and balance disturbances in PD.

4. Study Procedures

- a. Study design, including the sequence and timing of study procedures (distinguish research procedures from those that are part of routine care).

Subjects will be screened prior to enrollment by a study team member. The initial screening will be done over the phone to assess diagnosis and basic inclusion/exclusion criteria. Next, subjects will be asked to participate in an additional in-person screening during which participants will be asked to give written consent to participate in the study. After providing consent, the screening session will include:

1. Evaluations to determine the severity of PD symptoms based on the Movement Disorders Society Unified Parkinson's Disease Rating Scale (UPDRS) (Goetz et al. 2007).
2. Evaluations of cognitive function based on the Montreal Cognitive Assessment and the Frontal Assessment Battery (Nasreddine et al. 2005; Dubois et al. 2000).
3. A questionnaire to determine self-reported symptoms of PD-related motor impairment.

If the subject is a patient of co-investigator ([name]), the in-person screening may take place in the Johns Hopkins Parkinson's Disease and movement Disorder Center. Otherwise, it will take place in the Motion Analysis Lab at Kennedy Krieger Institute.

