Subjects who meet the inclusion/exclusion criteria for participation in the study will subsequently be asked to come to the Motion Analysis Lab at Kennedy Krieger Institute for 6 separate visits separated by one week. Each session will include an initial assessment of *Gait* and *Cerebellar Brain Inhibition (CBI)* measures preceding one 20-minute period of *tDCS*, followed by a second assessment of *Gait* and *CBI*. If participants experience discomfort due to *tDCS* or *TMS* and choose to discontinue the stimulation (see Section 8 for risks of discomfort due to these stimulation techniques), they will be allowed to continue the study with *Gait* assessments only.

Patients will be tested on and off their anti-Parkinson's medication (dopamine replacement or agonist). For the off testing, patients will abstain from taking their morning dose of medication and will have been off their medications for 12 hours. This is standard procedure for studies assessing PD patients (Bordelon et al. 2011).

Gait Testing

Prior to testing, small (dime sized) markers will be placed bilaterally on the foot (5th metatarsal head), ankle (lateral malleolus), knee (lateral joint space), hip (greater trochanter), pelvis (iliac crest) and shoulder (acromion process). These markers emit an infrared light which our sensors can track in 3D. A Northern Digital OPTOTRAK movement measurement system (with 2, 3-D position sensors) will be used to collect the 3-dimensional location of each marker. Marker position and analog data (treadmill belt speeds) will be time locked using OPTOTRAK software, and sampled simultaneously at 100 Hz and 1000 Hz, respectively.

Overground walking will be assessed using the Timed-Up-And-Go test (TUG) and 10 meter walk test. Next, subjects will walk on a treadmill for 2 minutes at their self-selected comfortable walking speed. During treadmill walking, subjects will wear a safety harness, have 2 safety cutoff switches (one large button to press, one magnetic cutoff tethered to them which stops the treadmill if they move too far back on it), and will have the option to hold onto a handrail if needed.

Additionally, standing balance will be assessed using Kistler force plates which allow measurement of the motion of the center of pressure. We will ask subjects to stand for 20 seconds in the following conditions: eyes open feet together and eyes closed feet together.

Transcranial Magnetic Simulation: Cerebellar Brain Inhibition

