Increased intracranial pressure, such as after infarctions or trauma.

Currently taking tricyclic anti-depressants or neuroleptic medication.

History of head trauma.

History of respiratory disease.

Dementia (Montreal Cognitive Assessment < 26; Frontal Assessment Battery < 13).

Orthopedic or pain conditions.

Pregnancy.

It is possible for an individual to be more susceptible to seizures than normal without being aware of the fact. Before giving their consent to participate, the participants will be questioned about their recent alcohol intake, and excluded if they have drunk more than 3 units of alcohol or taken other recreational drugs in the 24 hour period prior to testing, or if they are sleep deprived, all factors known to reduce cortical levels of inhibition and increase the risk of a seizure. The information gathered will be used exclusively for determination of inclusion/exclusion criteria and research, and will not be made public.

6. Drugs/ Substances/ Devices

- The rationale for choosing the drug and dose or for choosing the device to be used.

TMS and tDCS are non-invasive brain stimulation techniques used in an increasing number of studies in the last 20 years to understand cortical physiology or modulate brain function. These forms of stimulation are considered to be safe and of non-significant risk due to the short duration and the very low stimulation intensity. Dosage of tDCS is selected to safely elicit changes in motor-evoked potentials or behavioral outcome based on prior literature (Nitsche and Paulus, 2000; Nitsche et al., 2003a; Galea et al., 2011).

- Justification and safety information if FDA approved drugs will be administered for non-FDA approved indications or if doses or routes of administration or participant populations are changed.

N/A

- Justification and safety information if non-FDA approved drugs without an IND will be administered.

N/A

7. Study Statistics

- Primary outcome variable.

1. Stride length and gait speed during walking

2. Measures of corticomotor excitability (TMS)

- Secondary outcome variables.

Interlimb coordination during walking, variability of gait, cadence

- Statistical plan including sample size justification and interim data analysis.

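### The alcohol question is timed before consent, but the exclusion it serves covers the 24 hours before testing, which takes place at six later weekly visits

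*Combined protocol and SAP*

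**What the plan says.** Section 5 ends with a paragraph on temporary states that raise seizure risk. It sets the time of asking: "Before giving their consent to participate, the participants will be questioned about their recent alcohol intake". Participants are then "excluded if they have drunk more than 3 units of alcohol or taken other recreational drugs in the 24 hour period prior to testing". The sentence goes on to add a third ground and to give the reason for all of them: "or if they are sleep deprived, all factors known to reduce cortical levels of inhibition and increase the risk of a seizure". The alcohol and drug criterion thus has a 24-hour window counted back from testing. Sleep deprivation has no stated window.

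Section 4a places consent at an in-person screening, at which "participants will be asked to give written consent to participate in the study". It continues: "After providing consent, the screening session will include", followed by a rating of Parkinson's severity, cognitive tests and a symptom questionnaire. No TMS or tDCS is listed there.

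Stimulation comes later. "Subjects who meet the inclusion/exclusion criteria for participation in the study will subsequently be asked to come to the Motion Analysis Lab", and the attendance is "for 6 separate visits separated by one week". "Each session will include an initial assessment of" gait and cerebellar-brain inhibition (CBI, measured with paired-pulse TMS), then 20 minutes of active or sham tDCS, then both assessments again. Section 4b repeats the six weekly sessions, and Section 10 pays for screening separately from six later sessions.

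**The concern.** Recent alcohol, recent drug use and lack of sleep change from day to day. An answer given at screening says nothing about a participant's state weeks later, when the stimulation is delivered. The protocol gives seizure risk as its reason for these exclusions, so the day of stimulation is when the answer matters. Followed as written, the stated timing does not deliver that safeguard at most visits.

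The same paragraph says these states lower cortical inhibition. Section 7 makes corticomotor excitability measured by TMS a primary outcome, so an unchecked state could also add visit-to-visit noise to that measure. The documents give no figure from which to size this, and the point does not depend on it.

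**Working it through.** The plan states no figure to reproduce. The check is a reading of the sections together with calendar arithmetic.

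**Inputs**

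| Input | Value | Source |
|---|---|---|
| Time of the alcohol question | before consent | Section 5 |
| Window for alcohol and drugs | 24 hours (1 day) before testing | Section 5 |
| Consent | at screening, before visit 1 | Section 4a |
| Stimulation visits | 6, spaced 7 days apart | Sections 4a, 4b, 10 |
| CBI (TMS) assessments per visit | 2, before and after tDCS | Section 4a |
| Planned participants | 15 needed, 20 recruited | Section 7 |
| Gap g from the question to visit 1, in days | not given; 0 or more | assumption, full range shown |

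**Step 1: which visits can one question cover?** Put visit 1 on day 0. Visit k falls on day 7(k − 1), so the visits fall on days 0, 7, 14, 21, 28 and 35. The time from the question to visit k is g + 7(k − 1) days, and the visit is covered only if this is 1 day or less.

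- Visit 1 (k = 1): covered only if g ≤ 1.
- Visits 2 to 6: the time is at least 7 days, so they are never covered. For visit 6 it is at least 35 days.

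**Step 2: counts**

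| | g ≤ 1 day | g > 1 day |
|---|---|---|
| Visits covered | 1/6 = 16.7% | 0/6 |
| Visits not covered | 5/6 = 83.3% | 6/6 |
| TMS assessments not covered, per participant | 5 × 2 = 10 of 6 × 2 = 12 | 12 of 12 |
| Visits not covered, 15 completing | 15 × 5 = 75 of 15 × 6 = 90 | 90 of 90 |
| Visits not covered, 20 completing | 20 × 5 = 100 of 20 × 6 = 120 | 120 of 120 |

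The totals fall if participants drop out or, as Section 4a allows, go on with gait assessments only. Section 4b lists eight condition labels under its six sessions. That is a separate inconsistency. If there were eight weekly visits, the uncovered share would be at least 7/8 = 87.5%, so the conclusion would stand.

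**Step 3: could testing mean the screening assessments?** This reading does not fit. The stated reason is seizure risk, and screening lists no stimulation. Section 4a also describes the on- and off-medication visits as testing.

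**Step 4: is a later check stated elsewhere?** None was found.

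- Section 4a sets a 12-hour condition for medication before off-medication visits, and nothing comparable for alcohol, drugs or sleep.
- Section 4f allows removal where continuing would do harm or where fatigue prevents participation. It does not say when anyone asks about these states.
- Section 8b has a researcher present throughout but describes no such question.

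**The case against.** The strongest reply is that this is silence, not contradiction. The exclusion itself is tied to testing, so it can be read as applying before every visit, with the pre-consent question as a first screen only. The text does not say that the question is asked just once, and staff may well repeat it. That is a fair limit: the documents do not show that a check is absent in practice. But this reading supplies a repeat check that the text never states, and the one time of asking that is stated misses the window at most visits.

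Four further points carry some weight.

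- The contrast with medication is modest. The 12-hour rule also gives a window without saying how it is confirmed on the day.
- The pre-consent timing attaches expressly to alcohol. For drugs and sleep the text gives no separate time of asking, which leaves them with the same time or with none.
- The totals across participants only multiply one fact, a single stated question against six weekly visits. They are not additional evidence.
- The consequence is limited. Section 8b calls seizure with single-pulse TMS very rare and cites 3 possibly related cases, all in patients with epileptogenic lesions. The roughly 10 cases in Section 8c concern repetitive TMS, whereas this protocol describes single and paired pulses. Section 5 also excludes seizure history, family history of epilepsy, brain injury and head trauma.

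The last point lowers the stakes but does not remove the inconsistency. Section 5 introduces the questioning because people can be unusually prone to seizure without knowing it, which exclusions based on known history cannot detect. Section 8c accepts that a seizure cannot be ruled out even within accepted stimulation settings.

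**Conclusion.** The concern holds. The only stated time of asking can lie in the 24 hours before visit 1 at most. At least 5 of 6 stimulation visits (83%) have no stated question in the criterion's own window, rising to 6 of 6 if screening is more than a day before visit 1. This rests on six weekly visits, on consent preceding visit 1, and on reading testing as the stimulation visits. The counts describe what the protocol states; they measure neither what staff do nor adverse events. The absolute risk is small and cannot be quantified from the documents. The text should be corrected because the gap lies in a safeguard that the protocol sets for itself.

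**What to change.** The sponsor and the investigator should reconcile Sections 4a and 5 so that the stated timing of the questioning agrees with a window counted back from testing. The reconciled text should make clear how that timing applies to recreational drugs and sleep deprivation as well as alcohol, since the three share one sentence and one rationale. No threshold or clinical rule is proposed here.

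The cost is a wording edit in two sections and possibly a little added work around visits. Outcomes, sample size and analysis do not change.

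A separate editorial matter can be settled in the same revision: Section 8b excludes people with migraine or with severe or frequent headaches, but the Section 5 list does not name this exclusion. The two sections should be reconciled.

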Experimental sessions will be performed in a laboratory with easy accessibility to reduce risk of falls. A researcher will accompany participants at all times. We do not expect that a discontinuation will occur once a subject meets the admission criteria. However, the following reasons may motivate termination of a subject's participation in the protocol: the subject's poor compliance with protocol evaluations or examinations, or a subject's request to withdraw.

Other risks

The risks of withholding Parkinson's medication are feeling uncomfortable due to exacerbated Parkinson's symptoms (e.g. postural instability, bradykinesia, rigidity, etc.). Since we will only recruit patients with mild-moderate impairment, we anticipate that this discomfort in the off-medicated state will be minimal.

The risks of being harmed by the treadmill, overground walking assessments, or Optotrak markers is very low. Subjects may become fatigued or lose their balance during overground or treadmill walking, and have slight muscle soreness after walking. Other than that, the risks are no greater than normal walking. There is a small risk of the subject being allergic to the adhesive tape used to secure the Optotrak markers. There is potential risk of loss of confidentiality, as well as a potential risk for lost time from work. Additionally, there is a risk of getting tired or bored during questioning/answering of questionnaires.

Subjects will be placed in a safety harness that is connected to a ceiling mounted safety track during all testing on the treadmill so that they cannot fall. Subjects also will be tethered to a magnetic safety cut-off switch, which when pulled, stops the treadmill (e.g. if they move too far back on the treadmill). Additionally, subjects have a safety stop button mounted to the front handrail of the treadmill. All subjects are allowed to hold on to the handrail through the duration of all experiments and are asked to practice stopping the treadmill with the safety button. Recent data has shown that holding onto the handrail can create an unnatural walking pattern. Since we are studying walking patterns, individuals who are comfortable walking on a treadmill without holding onto the handrail may be asked not to hold on. An experimenter will stand next to the subject on the treadmill at all times and will have a safety cutoff button too.

We will also stop the treadmill and give a rest break when subjects feel fatigued, short of breath, or simply want a break. They will be allowed to stop any test at any time, or rest between tests. We also do not recruit subjects who have medical conditions that would make walking dangerous or uncomfortable. We will put a gait belt on all subjects as they walk overground and 1-2 investigators will walk behind them in case they lose their balance.

To reduce the risk of irritation from the tape we will ask before applying the tape to be if they have any known allergy. If they think they may have an allergy we will attempt to use athletic tape or co-band wrap to hold the markers in place during the experiment.

To reduce the risk of loss of confidentiality we give every subject a code that will connect them to their personal health information (PHI) that will be locked in our file cabinets. Only the researchers and PI will know where the key is. Any experimental information will only have the code name attached to it and will be locked in our password database on our computers.

To reduce the risk associated with loss of time from work or school we will be as flexible as possible with scheduling.

c. Plan for reporting unanticipated problems or study deviations.

Adverse events and protocol deviations will be reported to the primary investigator, to the KKI Office of Research Compliance, and to the JHM IRB using the appropriate adverse event reporting form.

Expected adverse events due to TMS or tDCS that will be reported in annual reviews:

1. Slight discomfort lasting less than a second on the scalp near the TMS coil.
2. Twitching of the face and jaw due to the magnetic pulse, which may be unpleasant but usually not painful.
3. Transient headache.
4. Itching sensation under the electrode (tDCS)
5. Phosphene-like visual phenomenon if the DC stimulation will be switched on or off rapidly

Exceptional adverse events due to TMS or tDCS that will be reported immediately:

1. Skin burn
2. Seizures have been reported using repetitive TMS in about 10 human subjects, out of several thousands tested all over the world. The appearance of a seizure during application of TMS with stimulation parameters regarded as safe cannot be excluded, therefore we defined appearance of a seizure as an exceptional adverse event.

d. Legal risks such as the risks that would be associated with breach of confidentiality.

We see minimal risk to confidentiality—data are coded and no identifying information is used in any analyses or publication. The master list containing the link between the data and the identity is kept on a computer that is double password protected. All health information, as well as study data, gathered at the time of the study, are kept in locked files, accessible only to study personnel. We adhere to all HIPAA privacy rules that affect research protocols.

e. Financial risks to the participants.

There are minimal financial risks to the participant. The risks include lost time from work and travel expenses.

9. Benefits

a. Description of the probable benefits for the participant and for society.

- i. Individual participant.

There are no direct benefits to participants.

- ii. Society

This study will help provide a better understanding of the role of the cerebellum in Parkinson's disease. In the future, this research may aid in the development of treatment for people with PD.

10. Payment and Remuneration

- a. Detail compensation for participants including possible total compensation, proposed bonus, and any proposed reductions or penalties for not completing the protocol.

The subjects will be paid \$25.00 for the initial screening session and \$50.00 for each of the six subsequent sessions. They will also have free valet parking for each visit. There is no penalty for not completing a session.

11. Costs

- a. Detail costs of study procedure(s) or drug (s) or substance(s) to participants and identify who will pay for them.

There is no cost to the subjects for participating in the study.
